6.3 HANDLING OF MISSING DATA

We will make every effort to collect all PRO data from study participants. We will collect these data in-person at the DFCI clinic visit closest to 180 Days (and additionally at earlier time points according to the results of 17-088) which, as compared to a mailed design, will help assure compliance. If a QOL survey is not completed, the PI or co-PI will personally contact each patient to ensure return at the next clinic visit. If patients do not complete the PROs despite personal contact by the PI, they will be regarded as non-responders (dropouts). We will record

Version 8 , 11/16/2020

[figure not shown]
all reasons for dropouts, and account for all patients in reports, whether or not they have dropped out. Of note, those who do not agree to participate (~30%) for the PRO assessment will not be regarded as missing.

We will take a standard approach to handling individual missing items on PROs that are received. For example, if item(s) are unanswered in FACT-BMT, subscale scores will be prorated by multiplying the sum of the subscale by the number of items in the subscale and then dividing by the number of items actually answered. Multiple imputation is a well-known approach for handling missing data. While this approach is a valid method for imputing missing independent variables to preserve study power, imputing outcome variables is more difficult, as this may introduce bias into the study conclusions. We will thus take several

approaches to handling missing data from dropouts. First, to assure PRO scores for non-responders are missing at random, we will perform a sensitivity analysis comparing the patient, HCT characteristics, and clinical outcomes between responders and non-responders. Second, we will perform multiple imputation on the outcome variable (including all independent variables) and compare the result without multiple imputation (i.e., inclusion of responding patients only). More importantly, with voluntary patient consent to participate in the study and proactive collection of survey data by the research team, we anticipate that the non-compliance rate will be minimal (<5%). Moreover, we anticipate that there will be no missing independent variables in all HCT patient-related data as this data must be reported to the CIBMTR database by the DFCI/BWH HCT center. Finally, to assure the robustness of our results, we will compare the FACT-BMT scores of the randomized Usual Care cohort with the non-randomized usual care cohort.

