5.51 Instrument Administration

In addition to the standard data collection that is required for all patients who undergo HCT in the United States (CIBMTR)—including NRM and overall survival (OS)—all patients will be asked to complete PROs at 100 days and 180 days post-transplant, including any patients that prematurely terminate Shared Care for any reason. This was determined based on recommendations made by the modified Delphi panel of patients from a previous study (17-088). PROs will focus on assessing physical, social, and emotional wellbeing.

Version 8 , 11/16/2020

To understand the care that is received by individuals who choose not to be randomized, for those who consent, the study will track in parallel fashion their HCT-related outcomes and PROs. This will provide a non-randomized observational cohort which will be a second source of analysis and will also allow us to determine if there is a participation bias for those randomized. Given exuberant non-randomized (NR) enrollment and since NR participants are not included in our main analysis, we will cap the number of participants enrolled in the non-randomized arm at 1 patient per month. This will further lessen the burden of data collection with our limited resources and will allow us to better utilize the time of our research assistant involved in data collection. Patients declining randomization will receive usual care following HCT at Dana-Farber.

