6.2 PATIENT-REPORTED OUTCOMES (POWERED ON FACT-BMT)

Our primary hypothesis is that patients in the Shared Care group will have improved PROs compared to those in Usual Care due to a decreased burden of traveling and/or relocation to the HCT center. To investigate this hypothesis, the primary endpoint of this aim is powered by an expected improvement in FACT-BMT score between Shared Care to Usual Care 180 days post HCT. Of the total 324 patients who are randomized at study entry, we project that 80% will be alive at six months after allogeneic HCT and 70% will participate in the day 180 PRO assessment. These projections are based on survival data of DFCI HCT patients between 2012 and 2015, and the response rate from our prior survey regarding financial hardship experienced at 180 days after HCT described above (DFCI RR=72%; Table 5). This yields a sample size of 180. In a previous study of QOL for patients after allogeneic HCT, the mean FACT-BMT score at 100 days after HCT was 110 (± 20).¹⁹ Therefore, we believe a difference of 20 or more will be meaningful to show improved PROs at a similar time period (day 180). Extrapolating from this information, if the FACT-BMT score is 120 for Shared Care and 100 for Usual Care at 180 days post-HCT, there will be >99% power to detect this difference. If, however, the difference is 10, then there will be 90% power to detect this difference. This power calculation is based on asymptotic power of the Wilcoxon-Rank-Sum test against an alternative shift at the two sided significance level of 0.05, assuming the standard deviation of the difference is 20. An additional preliminary endpoint is expected difference in mean PSS-4, one of the potential quality of life surveys, score at day 180 post-HCT. In our financial hardship survey, the mean PSS-4 score for DFCI allogeneic patients (n=139) was 5.6 (± 3.2). Extrapolating from these data, if the difference in PSS-4 between the Shared and Usual Care groups is 2 with standard deviation 3.2, there will be 98% power to detect this difference at the two-sided significance level of 0.05.

Table 3. Sample DFCI Allogeneic HCT Patient Characteristics (n=139)

Patient Characteristics	%*
Diagnosis	
Acute Myeloid Leukemia	35
Myelodysplastic Syndromes (MDS)	20
Myeloproliferative Neoplasms	15
Acute Lymphoblastic Leukemia	15
Other	15
Sex	
Female	41
Male	59
Age	
60 or under	50
Over 60	50
Race	
White	96
Non-white	4
Insurance Type	
Employer sponsored	64
Government sponsored	29
Self-insured	7

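### Section 6.3 keeps the projected ~30% of PRO decliners out of the missing data, so on its plain reading the planned checks reach about 9 of 87 survivors without a day-180 FACT-BMT score

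*Combined protocol and SAP*

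**What the plan says.** Section 6.2 builds the sample for the FACT-BMT comparison from the 324 randomised patients: "we project that 80% will be alive at six months after allogeneic HCT and 70% will participate in the day 180 PRO assessment". It continues: "This yields a sample size of 180". The 70% rests on the response rate of a prior survey (72% at DFCI). Section 5.51 exempts nobody: "all patients will be asked to complete PROs at 100 days and 180 days post-transplant, including any patients that prematurely terminate Shared Care".

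Section 6.3 then classifies patients without a score.

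- Non-completers: "If patients do not complete the PROs despite personal contact by the PI, they will be regarded as non-responders (dropouts").
- Reporting: the team will record "all reasons for dropouts, and account for all patients in reports, whether or not they have dropped out".
- Decliners: "Of note, those who do not agree to participate (~30%) for the PRO assessment will not be regarded as missing".

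The remedies that follow are introduced as "approaches to handling missing data from dropouts. First, to assure PRO scores for non-responders are missing at random". The first compares characteristics and clinical outcomes of responders and non-responders. The second imputes the outcome and will "compare the result without multiple imputation (i.e., inclusion of responding patients only"). Section 6.3 also expects non-compliance below 5%, citing consent to the study and active collection. It does not say 5% of whom.

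**The concern.** The 30% in section 6.3 is the complement of the 70% in section 6.2, and section 6.2 applies that 70% to surviving randomised patients. These are therefore trial participants with an assigned arm and no outcome. Declaring them not missing takes them out of the only two missing-data checks in the plan. Most of the projected non-response would then go unexamined.

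The boundary is also unclear, because a patient who declines is also a patient who does not complete. One analyst could impute about 9 patients and another 78 or more, and both could cite section 6.3.

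What is at stake is bias. Patients know their arm, because it decides where they are seen. PROs are collected at DFCI visits: Usual Care patients have all their visits there, Shared Care patients about half. The documents do not show that response will differ by arm, but the plan should be able to detect it if it does. If response and the unseen scores differ between arms, part of the FACT-BMT difference would reflect who answered.

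Separately, comparing observed characteristics cannot establish that scores are missing at random, since that condition concerns scores nobody has seen.

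**Working it through.** **Inputs.** 324 randomised, 80% alive, 70% participating, difference 10, SD 20, two-sided 0.05, Wilcoxon rank-sum (section 6.2); 1:1 allocation (section 5.1); ~30% decliners and <5% non-compliance (section 6.3).

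**1. Reproduce the plan's figures.**
- Survivors: 324 × 0.80 = 259.2.
- With a score: 259.2 × 0.70 = 181.4 (plan: 180).
- Power with 90 per arm: effective n = 90 × 3/π = 85.9; SE = 20 × √(2/85.9) = 3.05; 10/3.05 − 1.96 = 1.32, giving 90.6% (plan: 90%).

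Both agree with the plan.

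**2. Survivors without a score.** 259.2 × 0.30 = 77.8, about 78. At the survey's own 72%, 259.2 × 0.28 = 72.6, about 73.

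**3. What the 5% can mean.**
- As total non-response among survivors: 259.2 × 0.95 = 246.2 scores. This does not fit the plan's 180.
- As non-compliance among those who agreed: 181.4 × 0.05 = 9.1 further patients at most. This fits the 70% and the ~30%.

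Only the second is compatible with section 6.2.

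**4. Reach of the planned checks on that reading.**
- Total non-response: 1 − 0.70 × 0.95 = 33.5%; 259.2 × 0.335 = 86.8 patients.
- Covered by the comparison and imputation: 9.1/86.8 = 10%.
- Not covered: about 78.
- Power if the further 9 are lost: 181.4 × 0.95 = 172.4 scores, giving 89.4% by the same formula.

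**5. Possible bias (illustration; r and g are assumptions, not from the documents).** Let r be an arm's response rate and g its responder minus non-responder mean. The responder-only difference departs from the all-survivor difference by (1 − r_S)g_S − (1 − r_U)g_U.
- r 0.70/0.70, g 10/10: 3 − 3 = 0.
- r 0.65/0.75: g 10 gives 3.5 − 2.5 = 1; g 20 gives 7 − 5 = 2.
- r 0.60/0.80: g 10 gives 4 − 2 = 2; g 20 gives 8 − 4 = 4.
- r 0.70/0.70, g 20/10: 6 − 3 = 3; g 20/0: 6 − 0 = 6.

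The plan's own scenarios are differences of 10 and 20 points.

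**The case against.** A reader might infer that sections 6.2 and 6.3 contradict each other outright. They need not. If about 30% decline and under 5% of the others fail to complete, every percentage is consistent. That objection stands. What remains is an unstated denominator and a blurred boundary. The reconciling reading also sits awkwardly with the text, because the 5% is justified by consent to the study, which every randomised patient gave.

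Parts of the remedy are already planned. Section 6.3 promises to record reasons for dropout and to account for all patients. If decliners count as dropouts under its own definition, the checks could reach everyone. The sentence on decliners points the other way, so the plan does not settle it.

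The 78 is a projection from a survey response rate. In-person collection with personal follow-up may do better.

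The time of refusal is not visible, and the consent pages are not available. An opt-out fixed before randomisation would mainly limit generalisability. Against that, section 6.2 uses a day-180 response rate, and section 5.51 asks all patients. The ~30% also does not match refusal of the trial itself, for which Table 2 assumes 80% agreement. An unseen opt-out would not make the wider analysis harmful.

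Finally, section 6.3 warns that imputing outcomes may introduce bias, and imputation under missing at random removes only what recorded variables explain. This is fair. It is why the wider imputation belongs beside the responder-only result, with a further analysis for unseen differences.

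**Conclusion.** The point holds as a gap in the definition and handling of missing data. On the plain reading of section 6.3, about 78 of 259 projected randomised survivors fall outside both planned checks. Those checks reach about 9 of 87 survivors without a score (10%), and the powered comparison is responder-only with no check on most of the non-response. These figures rest on the plan's 80% and 70%, and on 5% as the upper limit among those who agreed.

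Two stronger inferences are not supported. The trial is not shown to be underpowered: n=180 already allows for 30% non-participation, the 90% reproduces, and losing a further 9 leaves 89.4%. Nor is the FACT-BMT result shown to be biased: the documents give neither response by arm nor any non-responder scores. The 0 to 6 points above are illustration only, and zero is among them.

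This should be corrected before analysis. Confidence is moderate, because the time of refusal cannot be seen. Patients who die before day 180 (324 × 0.20, about 65 projected) are a separate question.

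**What to change.** 1. Delete the sentence on decliners in section 6.3. Count every randomised patient alive at day 180 without a FACT-BMT score as missing. If any patients opted out of PROs before randomisation, report them separately.
2. State that the 5% applies to those who agreed, and that total expected non-response among survivors is about 30–34%.
3. Report response by arm, with reasons where recorded.
4. Apply the planned responder/non-responder comparison and multiple imputation to all these patients, as a sensitivity analysis beside the responder-only result. State which result is primary. Include arm, the Table 4 attributes (which contain conditioning intensity), site (a stratification factor in section 5.1) and day-100 FACT-BMT where available.
5. Replace the claim to establish missing at random with wording that the comparison describes observed differences only. Add a simple pre-stated delta-adjusted sensitivity analysis for differences that imputation cannot address.

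**Cost.** SAP wording and slightly more analysis work, with no new outcome data. Recording decliners' reasons may be a small addition. The stated non-response figure becomes less favourable, and imputed intervals may be wider. The day-100 score does not help for patients who decline at both times.

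### Section 6.3 cannot establish that missing FACT-BMT scores are missing at random, and none of its checks would detect arm-specific, score-dependent non-response

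*Combined protocol and SAP*

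**What the plan says.** Section 6.3 (Handling of Missing Data) has three checks that bear on missing PRO scores.

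1. A comparison of observed variables that sets responders against non-responders: "to assure PRO scores for non-responders are missing at random, we will perform a sensitivity analysis comparing the patient, HCT characteristics, and clinical outcomes".
2. Imputation of the outcome: "we will perform multiple imputation on the outcome variable (including all independent variables) and compare the result without multiple imputation", the latter meaning responders only.
3. A closing check: "to assure the robustness of our results, we will compare the FACT-BMT scores of the randomized Usual Care cohort with the non-randomized usual care cohort".

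The section also warns that "imputing outcome variables is more difficult, as this may introduce bias into the study conclusions", and it promises to record "all reasons for dropouts, and account for all patients in reports, whether or not they have dropped out".

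On how much will be missing, the text points two ways. Section 6.3 expects non-compliance below 5%, yet it also says that "those who do not agree to participate (~30%) for the PRO assessment will not be regarded as missing". Section 6.2 sizes the trial on 80% survival at six months and 70% participation in the day-180 assessment.

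On collection, Section 6.3 says: "We will collect these data in-person at the DFCI clinic visit closest to 180 Days".

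No delta-adjusted, pattern-mixture, tipping-point or other analysis that departs from MAR appears in the document.

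**The concern.** MAR is a statement about the score nobody saw, given what was seen. A table of observed characteristics holds no information on that score once those characteristics are accounted for. A difference in the table is evidence against missing completely at random. The absence of a difference is not evidence for MAR.

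The imputation check does not fill the gap. Standard multiple imputation assumes MAR given its covariates. The responders-only rank-sum test, on which Section 6.2 bases its power, uses no covariates and needs the stronger condition that response is unrelated to the score within each arm. If response depends on the unseen score, both are biased, usually in the same direction, and their agreement says little.

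Score-related non-response is plausible because forms are completed in person at DFCI, and patients who feel worst may be least able to attend. It could differ by arm. Usual Care patients attend DFCI for every scheduled visit and Shared Care patients for about half (Section 5.5). In the Appendix K example, the DFCI visits nearest day 180 fall on days 156 and 184. At stake is the FACT-BMT comparison at day 180, the outcome on which the PRO aim is powered.

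**Working it through.** **The plan's own figures (Section 6.2).** Evaluable patients: 324 × 0.80 × 0.70 = 181.4, stated as 180, so 90 per arm. Power for 10 points with SD 20 at two-sided 0.05 is 91.8% by the normal formula, and 90.6% with the rank-sum efficiency 3/π applied to n (stated: 90%). These reproduce and are not in dispute.

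**Bias formula.** Let m be the share of survivors in one arm without a score, and g the gap between mean scores of responders and non-responders in that arm. The responder mean exceeds the survivor mean by m × g. If the other arm has no such gap, the between-arm bias is m × g. With SE = 20 × √(2/90) = 2.98 and no true effect, the normal approximation gives the figures below. The documents give no value for g, so it is shown over a range.

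| g (one arm) | m = 0.30: bias | false positives | m = 0.05: bias | false positives |
|---|---|---|---|---|
| 5 | 1.5 | 7.9% | 0.25 | 5.1% |
| 10 | 3.0 | 17.2% | 0.5 | 5.3% |
| 15 | 4.5 | 32.6% | 0.75 | 5.7% |
| 20 | 6.0 | 52.1% | 1.0 | 6.3% |

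The 5% columns keep the same SE. With 130 × 0.95 ≈ 123 responders per arm, the SE falls to 20 × √(2/123) = 2.55, and the last entry becomes about 6.8%.

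**Would the checks notice?** This was simulated with 1,500 trials per setting and 20 imputations pooled by Rubin's rules. From the plan: 324 × 0.80 / 2 ≈ 130 survivors per arm, 70% response, SD 20. Assumed: no true effect, covariates explaining 15% of score variance, and response odds multiplied by 1.5 or 2 per SD of the patient's own score in Shared Care. The Usual Care mechanism was varied.

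| Usual Care mechanism | Responder-only bias (odds 1.5 / 2) | Rank-sum false positives |
|---|---|---|
| random non-response | 2.4 / 3.8 | 12% / 25% |
| half strength (log-odds) | 1.1 / 1.8 | 7% / 8% |
| equal strength | about 0 | 4% to 5% |

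The figures are approximate; repeat runs of the first row at odds 2 gave 23% to 25%. In that row, imputation leaves a bias of about 2.0 or 3.3 points, so it removes only a small part. The responder/non-responder comparison flags a difference in roughly 9% or 13% of trials.

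A second simulation let response depend only on the part of the score that the covariates do not explain (Shared Care only, non-responders about 10.9 points lower). Responder-only and imputed estimates were both +3.33, false positives 20.3% and 20.7%, and the covariate comparison flagged 4.9% of trials, its chance rate.

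**What a tipping-point analysis would show.** With 91 responders per arm (130 × 0.70), the smallest significant difference is 1.96 × 20 × √(2/91) = 5.81. Holding the SE fixed, significance is lost when Shared Care non-responders score lower than assumed by (observed difference − 5.81) / 0.30:

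- observed 7: about 4.0 points
- observed 8: about 7.3 points
- observed 10: about 14.0 points

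So the same 30% missing leaves a 7-point result fragile and a 10-point result fairly secure. None of the planned checks would give the reader that information.

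**The case against.** **A reader might infer that imputation against responders only is the sole remaining check.** It is not. Section 6.3 also compares randomized with non-randomized Usual Care, and that is not an imputation under MAR. However, it contains no Shared Care patients, uses observed scores only, and mixes self-selection with non-response, so it cannot reveal this bias.

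**A reader might infer that imputation and the responders-only analysis share assumptions and covariates and are bound to agree.** The rank-sum test uses no covariates, so the contrast can expose missingness driven by observed variables, and the two estimates do differ somewhat in the simulation. That has value. It does not extend to dependence on the unseen score.

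**Perhaps little will be missing.** Section 6.3 expects non-compliance below 5%, and at that level the bias is at most about 1 point even with a 20-point gap. This stands as a limit on the size. But Section 6.2 projects 70% participation, and Section 6.3 does not regard the roughly 30% who decline the assessment as missing. Read literally, neither dropout check then covers the main exposure.

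**The mechanism may act in both arms.** All patients complete the forms at DFCI, so illness could suppress response equally, and the bias is then about 0. This also stands. The one-arm figures are an upper case within the odds shown.

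**The plan shows some awareness.** It concedes that imputing outcomes may introduce bias and records reasons for dropout. No analysis is tied to either.

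**Conclusion.** The point holds. The comparison of observed characteristics cannot do what Section 6.3 claims for it, and no planned analysis departs from MAR. A FACT-BMT difference biased by arm-specific, score-dependent non-response could therefore look robust.

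It would go too far to say that it would look robust: the plan sets no robustness criterion, and if MAR holds given the covariates, the imputation is valid. The documents also do not support reading the 25% as an expected error rate. It requires 30% missing, dependence on the patient's own score in one arm only, odds of 2 per SD, and covariates explaining 15% of the variance. Apart from the 30%, which follows from the Section 6.2 projection, these are assumptions. Across the settings simulated, the responder-only bias runs from about 0 to about 3.8 points, against the 10-point difference for which Section 6.2 quotes 90% power. This should be corrected, because the remedy is cheap and is credible only if fixed before the results are seen.

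**What to change.** In Section 6.3:

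- Replace the claim to assure MAR with a statement that the comparison describes differences between responders and non-responders. State MAR as an assumption of the imputation.
- In the sensitivity analyses, count every randomized survivor without a day-180 FACT-BMT score as missing, including those who declined the PRO assessment.
- Pre-specify a delta-adjusted (tipping-point) multiple imputation that shifts imputed scores separately by arm over a range, for example 0 to 20 points. Report the shift at which the FACT-BMT conclusion changes, and let readers judge how plausible it is. A fixed pass/fail threshold is not needed, and nothing in the documents supports a particular value.

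The cost is revised wording and a few lines added to the imputation code, with no new data. The downside is a little more analysis and a result that may look less firm.
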